
• doesn't have a well visit scheduled in the next 45 days• has not had a well child visit > 365 days	
• doesn't have a well visit scheduled in the next 45 days• has not had a well child visit in 365 days

• have English and/or Spanish as preferred language	• have English and/or Spanish as preferred language
---	---

Factors under study (levels):

Personal Contacts (12-14 month & 4-year-olds) Trial:

Number of automated messages sent prior to any personal contact attempts (1 vs. 2)

Number of personal contact attempts made by medical assistant (0 vs. 1)

	1 automated message sent	2 automated messages sent
0 personal contact attempt		
1 personal contact attempt		

MyChart Trial:

Families enrolled in MyChart will be selected and randomized into the following groups:

	no message	1 MyChart message sent	2 MyChart messages (e.g. Mon and Thurs)
Low Tailored Message			
High Tailored Message			

Number of messages (0 vs. 1 vs. 2); Type of messages (low tailored message with name only vs. high tailored message with date of last WCC and age included)

Televox (age 6-11yo) Trial:

Patients will be randomized into the following three groups. Patients with MyChart are excluded:

no message	Low Tailored Message 2 automated standard messages sent (e.g. Thu, Fri)	High Tailored Message 2 automated tailored messages sent (e.g. Thu, Fri)
------------	--	---

Televox (age 12-17yo) Trial:

Patients will be randomized into the following three groups:

no message	Low Tailored Message 2 automated tailored messages sent (e.g. Thu, Fri)	COVID Tailored Message 2 automated messages sent (e.g. Thu, Fri)
------------	--	---

Automated Message: Parents indicate their preferred mode of reminder (e.g. call or text message) when they schedule appointments. Cincinnati Children's uses a HIPAA compliant platform called TeleVox to send automated calls and text reminders to parents according to their preferences which are recorded in the Electronic Health Record (EHR).

Here is the script for **low tailored automated messages** that will be sent via call or text:

Clinic	Message 1*	Message 2*
---------------	-------------------	-------------------

HPC	Hi! Hopple misses you! (INSERT FIRST NAME) is due for a checkup. Please call [contact], option 1 to schedule a visit as soon as possible.	Hi! If you haven't already, please call [contact], option 1 to schedule (INSERT FIRST NAME)'s upcoming visit at Hopple.

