PPC	
Hi, this is [Staff First Name] from PPC. [Pt first name] is due for a check up. I'll call in a day or two to help schedule that appointment or you can walk in today to have your child seen! You can also call [contact], option 1 to schedule.
	
Hi, this is [First Name] from PPC. I noticed that [Child's First Name] is due for a check up. Can I schedule that for your right now?
 
Alternate script for leaving a voice message: Hi, this is [First Name] from PPC. I noticed that [Child's First Name] is due for a check up. Sorry I missed you. Please call [contact], option 1 to schedule your appointment or walk in today to have your child seen.

*Scripts have been translated into Spanish versions by Interpreter Services

Response variables (outcomes):

- Appointment **was scheduled** within 2 weeks of intervention (Y/N) (date of actual appointment may be greater than 2 weeks from intervention)
- Appointment **was completed** within 8 weeks of intervention (Y/N). Appointment completed within 8 weeks of randomization will be used for group who does not receive any intervention.
- (Primary Outcome) Receipt of MMR by 15 months of age or receipt of 2nd MMR dose by 3 months after randomization (Y/N)
- Receipt of 1st COVID vaccination (ages 12-17 years) within 8 weeks of first intervention (Y/N)
- Family member receipt of COVID vaccination in our health system within 8 weeks of first intervention

Blocking: (controlling for factors that might influence the outcome)

- Age (12-14 months, 4 years)
- Clinic location (PPC, HPC, FPC)

Personal Contacts (12-14 months & 4-year-olds) Trial:

Randomization: Eligible patient will be identified by running a report in the electronic health record (EHR). We will run this report, stratified by clinic location, and randomly assign patients into one of the four groups created by our 2 X 2 design. Groups will receive their assigned intervention in one of four successive weeks with the sequence randomly assigned (see table below).

Replication: We will conduct a total of 3 trials, repeating the randomization procedure every 4 weeks to identify children who become eligible: Weeks 1-4 = trial #1, weeks 5-8 = trial #2, weeks 9-12 = trial #3.

	1 automated message sent	2 automated messages sent
--	---------------------------------	----------------------------------

0 personal contact attempt	Message sent on Thu (weeks 3, 5, 10)	Message sent on Thu & Fri (weeks 4, 6, 12)

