1 personal contact attempt	Above plus attempt Mon – Fri of following week (weeks 2, 7, 11)	Above plus attempt Mon – Fri of following week (weeks 1, 8, 9)

MyChart and Televox Trials (6-17 years old):

Randomization: Eligible patients will be identified by running a report in the electronic health record (EHR). We will run this report, stratified by clinic location, and randomly assign patients into one of the study groups as described above. Groups will receive their assigned intervention in one of four successive weeks with the sequence randomly assigned (see table below).

We will randomize children who are eligible and implement interventions for each trial : Weeks 1-3 = Televox Trial 12-17yo, Weeks 4-7 = Televox Trial 6-11yo, Weeks 8-10 = MyChart Trial.

MyChart Trial:

	no message	1 MyChart message sent	2 MyChart messages (e.g. Mon and Thurs)
Standard Message	No intervention	Week A	Week B
Tailored Message		Week A	Week B

Televox (6-11yo) Trial:

no message	Low Tailored Message 2 automated standard messages sent (e.g. Thu, Fri) (weeks C, C)	High Tailored Message 2 automated tailored messages sent (e.g. Thu, Fri) (weeks D, D)
-------------------	---	--

Televox (12-17yo) Trial:

no message	Low Tailored Message 2 automated tailored messages sent (e.g. Thu, Fri) (week A)	COVID Tailored Message 2 automated messages sent (e.g. Thu, Fri) (week B)
-------------------	---	--

Of note, automated messages and/or personal contact attempts will not be completed if the parent schedules an appointment after being randomized but before receiving the intervention.

Covariates for logistic regression: (factors that might influence the outcome if not be balanced across groups)

1. Child age at the time of randomization (rationale: visits are less frequent for children age 4 years)
2. Parent preference for call vs. text mode of contact (rationale: calls may be more likely to get blocked than texts)
3. Parent with activated MyChart account (Y/N) (rationale: not dependent on calling scheduling center to make appointment)
4. Access to appointment: Number of days to 3rd next available appointment at patient's clinic at time their first automated message is sent
5. Patient receipt of any past immunizations (Y/N) (rationale: vaccine refusing parents will be unlikely to change even if they return for well child check)

6. School-age vs. adolescent patient age (rationale: adolescents less likely to get yearly check-ups)
7. Historical no-show rate

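### Adolescents with MyChart can enter the MyChart trial while their Televox 12-17 eight-week window is still open, and the overlap differs by Televox arm

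*Protocol*

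**What the plan says.** All of this is in the protocol; the SAP covers only the Personal Contacts trial.

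- **Calendar** (MyChart and Televox Trials, Randomization): "Weeks 1-3 = Televox Trial 12-17yo, Weeks 4-7 = Televox Trial 6-11yo, Weeks 8-10 = MyChart Trial". The entry that matters most here is the last, "Weeks 8-10 = MyChart Trial".
- **Who may enter** (Factors under study): for Televox 6-11, "Patients with MyChart are excluded". The Televox 12-17 entry says only "Patients will be randomized into the following three groups". For the MyChart trial, "Families enrolled in MyChart will be selected and randomized into the following groups". The heading shared by the MyChart and Televox trials gives ages 6-17.
- **Outcome windows** (Response variables): completion is counted to eight weeks from intervention. For the untreated group, "Appointment completed within 8 weeks of randomization will be used for group who does not receive any intervention".
- **Message weeks**: in Televox 12-17, low tailored messages go out in week A and COVID tailored messages in week B. The order is random and the letters are not tied to calendar weeks.

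No rule covers a child who qualifies for both trials. There is no washout and no censoring at a second randomization. MyChart account status is listed as a covariate, but it enters a model only if the groups differ on it.

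**The concern.** An adolescent with MyChart can be randomized to Televox in weeks 1-3 and again to MyChart in weeks 8-10, before the first trial has finished counting that child's visits. Outreach from the second trial can then produce a visit credited to the first.

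Randomization does not protect the Televox comparison, because the arm itself sets the overlap. The two messaged arms are sent in different weeks, and the no-message clock starts at randomization. Adjusting for MyChart status at baseline would not repair this, since the extra exposure comes after randomization. The planned per-protocol analysis gives no rule for children who receive both kinds of outreach. At stake is eight-week visit completion in Televox 12-17, above all the 30% versus 40% contrast that sets that trial's sample size.

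**Working it through.** **1. The plan's own figure.** For 30% versus 40%, two-sided alpha 0.05, 80% power and pooled variance:

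n = [1.96·√(2·0.35·0.65) + 0.8416·√(0.30·0.70 + 0.40·0.60)]² / 0.10² = (1.3221 + 0.5646)² / 0.01 ≈ 356 per group.

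This matches the protocol's 356 per group and 1,068 in total.

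**2. Calendar.** Let Monday of week 1 be day 1. A Thursday message in week w falls on day 7(w − 1) + 4 and its window closes 56 days later. MyChart opens on Monday of week 8, day 50.

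| Start of window | Closes | Days left at day 50 |
|---|---|---|
| Message in week 1 | day 60 (Thursday, week 9) | 10 |
| Message in week 2 | day 67 (Thursday, week 10) | 17 |
| Message in week 3 | day 74 (Thursday, week 11) | 24 |
| No message, randomized day 1 | day 57 (Monday, week 9) | 7 |

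If MyChart messages went out on Monday of week 9 instead, 3, 10, 17 and 0 days would be left. The two-week scheduling windows close by Thursday of week 5, well clear of MyChart.

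**3. Who can still enter MyChart.** Children with a visit in the past 365 days, or one booked in the next 45, are ineligible. On the planned completion rates of 2%, 30% and 40%, about 98%, 70% and 60% have not completed a visit by the end of the window. I use these as rough shares still able to enter.

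**4. MyChart share (m).** The protocol does not give it. Its eligible counts are 1,000 (MyChart), 2,500 (Televox 6-11) and 1,100 (Televox 12-17). Assume equal uptake at all ages.

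- If the 2,500 already omits MyChart families, 2500·m/(1 − m) + 1100·m = 1000, so m ≈ 0.23.
- If it includes them, m = 1000/3600 ≈ 0.28.

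I also show an assumed 50%.

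**5. Gain per arm.** Four of the five MyChart groups receive messages. Their planned mean completion is (10 + 20 + 20 + 30)/4 = 20%, against 2% with no message, so the average lift is 0.8 × 0.18 = 0.144. Assume these completions are spread evenly over 56 days. With p the planned rate and d the days left:

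gain = (1 − p) × m × 0.144 × d/56

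For example, at m = 0.5 the no-message gain is 0.98 × 0.5 × 0.144 × 7/56 = 0.88 points. For low tailored sent in week 1 it is 0.70 × 0.5 × 0.144 × 10/56 = 0.90 points.

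| m | Low / COVID sent in week | Gain in points: none / low / COVID | COVID minus low | Power at 356 per group |
|---|---|---|---|---|
| 23% | 1 / 2 | 0.41 / 0.41 / 0.60 | 10.2 | 81.2% |
| 23% | 2 / 1 | 0.41 / 0.70 / 0.35 | 9.6 | 76.9% |
| 28% | 1 / 2 | 0.49 / 0.50 / 0.73 | 10.2 | 81.5% |
| 28% | 2 / 1 | 0.49 / 0.86 / 0.43 | 9.6 | 76.1% |
| 28% | 3 / 1 | 0.49 / 1.21 / 0.43 | 9.2 | 72.9% |
| 50% | 1 / 2 | 0.88 / 0.90 / 1.31 | 10.4 | 82.6% |
| 50% | 2 / 1 | 0.88 / 1.53 / 0.77 | 9.2 | 72.9% |
| 50% | 3 / 1 | 0.88 / 2.16 / 0.77 | 8.6 | 66.6% |

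**6. Direction against no message.** At 50%, a COVID arm sent in week 1 gains 0.77 points while no message gains 0.88, so the contrast shrinks by 0.11. A low tailored arm sent in week 2 gains 1.53, so its contrast grows by 0.65. With 14 days of overlap in every arm, 2/30/40% becomes 3.8/31.3/41.1%, and the no-message arm gains most.

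**The case against.** The strongest reply is that the effect is small and falls away from the trial's main question. Much of that stands.

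- The planned contrasts with no message are 28 and 38 points. No scenario above threatens them.
- The primary outcome, MMR, belongs to the Personal Contacts trial, and two-week scheduling closes before MyChart opens.
- Part of the asymmetry comes from the different time anchors and would shrink if those alone were aligned. The different message weeks of the two messaged arms would still leave some.
- MyChart messages could go out late enough in weeks 8-10 to miss some windows. The protocol does not fix this.

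A reader might also infer stronger points that the documents do not support.

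- **That the overlap systematically favours the messaged arms.** The no-message window can be open too, and more of those children remain able to enter MyChart. The sign depends on weeks the protocol leaves unmapped.
- **That the MyChart trial is contaminated unequally by arm, or that its no-message rate rises above the planned 2%.** A fresh randomization balances earlier Televox exposure in expectation. Entrants are mainly children who did not respond to Televox, which could as easily lower that rate.
- **That first COVID dose is biased in the same way.** Its eight-week window can overlap too, but no starting date is given for the no-message group, and the MyChart messages as described carry no COVID content.

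None of this supplies the missing rule on entering both trials.

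**Conclusion.** The point holds for eight-week visit completion in Televox 12-17. As written, the plan allows a second randomized outreach inside the first trial's outcome window, for a length of time that depends on the arm. The direction of the bias is not fixed.

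At a MyChart share of 23-28%, the change in any between-arm contrast is under 1 point. At an assumed 50% with messages in weeks 1 and 2, the powered 10-point contrast becomes about 9.2 or 10.4 points, with power near 73% in the worse order. Using week 3 widens the range.

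These figures rest on MyChart messages starting on Monday of week 8, control randomization on Monday of week 1, even spread of completions, the planned rates, and a MyChart trial that includes adolescents, as the 6-17 heading implies. The overlap itself needs only the last of these and a MyChart start early enough in weeks 8-10. It is worth correcting because correction is cheap, not because it endangers the main contrasts.

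**What to change.** Start the MyChart trial only after the last Televox 12-17 eight-week window has closed. With a last message in week 3 that means after week 11, so week 12 instead of week 8: a delay of about four weeks, in a study that runs to December 31, 2022. Count the eight-week outcomes in all Televox arms from the same date, and state in the protocol how a child eligible for both trials is handled. Adjusting the MyChart analysis for prior Televox arm is optional.

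Two other routes cost more. Excluding MyChart adolescents from Televox 12-17 leaves almost no slack: 1,100 − 1,068 = 32 children, or 2.9% of the pool. At an assumed 30% share, 770 would remain, about 256 per arm, with 66.1% power for 30% versus 40%. Dropping adolescents from MyChart would remove about 253 to 306 children (23-28% of 1,100) from a list of 1,000, when 1,465 are needed.

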8. Community rates of COVID based on 7 day moving average.

Power/Sample Size

Personal Contacts (12-14 month & 4-year-olds) Trial:

We based our hypotheses (see table, below) on a systematic review's pooled estimates of effect size for automated messages and personalized calls finding 37% and 40% of children, respectively, completed immunizations.¹ Because of the significant cost involved in making personal contacts, the minimal difference in outcome that would make it worth the effort is high.

Hypotheses	% of children who receive MMR by 15 months of age	
	1 automated message sent	2 automated messages sent
0 personal attempts	20% ^C	35% ^B
1 personal attempt	50% ^A	65% ^{AB}

We calculated sample size needed per group to detect a difference for each of the contrasts below with alpha of 0.05 and power of 80%.

Contrast	Sample Size per Group
A vs C	36
B vs C	136
A vs. B	167
A vs. AB	167
B vs. AB	40
C vs. AB	16

To fully power the 2 X 2 factorial trial, we estimate needing 167 per group X 4 groups = 668 total subjects. There are currently 712 children eligible for the study. More will become eligible every month so we expect to far exceed the required sample size after 3 replications. If needed, we could increase the number of replications of the trial to reach the targeted sample size. We acknowledge that we are not powered to precisely estimate any interactions between interventions.

MyChart Trial:

In hypothesis testing for 0 message vs. 1 message vs. 2 messages, we will do the testing in a fixed sequence - test 2 messages vs. 0 message first, only if it is significant then test 2 messages vs. 1 message, thus the type I error rate of 0.05 is retained. Since the hypothesis testing of 2 messages vs. 0 message would be considered easier to achieve than the hypothesis testing of 2 messages vs. 1 message, the power analysis for this trial should be based on the design of (standard message vs. tailored message) by (1 message vs. 2 messages). We based our hypotheses (see table, below) on previous work indicating approximately 20% WCC appointment completion on automated text reminders. We anticipate that a tailored message increases the WCC appointment completion rate by another 10%.

Hypotheses		% of children complete WCC within 8 weeks	
		1 automated message sent	2 automated messages sent
Standard Message	2%	10% ^C	20% ^B
Tailored Message		20% ^A	30% ^{AB}

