We calculated sample size needed per group to detect a difference for each of the contrasts below with alpha of 0.05 and power of 80%.

Contrast	Sample Size per Group
A vs C	199
B vs C	199
A vs. AB	293
B vs. AB	293
C vs. AB	62

We assume no difference between A vs. B and thus not consider powering the comparison between these two groups, but we will explore non-inferiority analysis for this comparison in data analysis. To fully power the above contrasts, we estimate needing 293 per group X 4 groups = 1172 subjects. Adding 293 in the zero message group, we would need a total of 1465 subjects. There are currently 1000 children eligible for the study. More will become eligible every month so we expect to exceed the required sample size after 2 replications. If needed, we could increase the number of replications of this trial to reach the targeted sample size. We acknowledge that we are not powered to precisely estimate any interactions between interventions.

Televox (6-11yo) Trial:

We calculated sample size based on the following hypotheses:

% of children complete WCC within 8 weeks		
no message	2 Low Tailored Messages	2 High Tailored Messages
2%	20%	30%

With alpha of 0.05 and power of 80%, to fully power the contrasts between the above groups, we need 293 per group X 3 groups=879 subjects. Currently there are 2500 kids eligible, so we expect to reach the targeted sample size.

Televox (12-17yo) Trial:

We calculated sample size based on the following hypotheses:

% of children complete WCC within 8 weeks		
no message	2 Low Tailored Messages	2 COVID Tailored Messages
2%	30%	40%

With alpha of 0.05 and power of 80%, to fully power the contrasts between the above groups, we need 356 per group X 3 groups=1068 subjects. Currently there are 1100 kids eligible, so we expect to reach the targeted sample size.

Analysis

We will conduct descriptive analyses to characterize the participants in terms of demographics and other potential covariates in consideration (child age group, parent's preference for call vs. text mode of contact, whether parent had activated MyChart account, access to appointment, whether patient receipt of any past immunizations, historic no show rate, and community rates of COVID). We will use chi square tests to examine whether participants in the 4 groups are similar in these characteristics.

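### The MyChart fixed sequence for 0, 1 or 2 messages has no step for 1 versus 0, and the Analysis section gives a different multiplicity scheme for the same trial.

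*Protocol*

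**What the plan says.** Protocol, Factors under study, MyChart Trial, defines a three-level factor: "Number of messages (0 vs. 1 vs. 2"). It is crossed with message type (low or high tailored).

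Protocol, Power/Sample Size, MyChart Trial, gives the testing rule for the three levels: "test 2 messages vs. 0 message first, only if it is significant then test 2 messages vs. 1 message". It concludes: "thus the type I error rate of 0.05 is retained". It then reasons that "the power analysis for this trial should be based on the design of (standard message vs. tailored message) by (1 message vs. 2 messages"), so none of the tabulated contrasts involves the no-message group. Sizes are chosen "to detect a difference for each of the contrasts below with alpha of 0.05 and power of 80" percent. The result is "we estimate needing 293 per group X 4 groups = 1172 subjects", followed by "Adding 293 in the zero message group, we would need a total of 1465 subjects".

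Protocol, Analysis, covers the MyChart and Televox trials together. It promises pairwise tests between the groups with p values adjusted for multiplicity. It does not name the method, mention the fixed sequence, or say whether the no-message group is in the set.

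The SAP covers only the 2x2 personal-contact trial (section 1, Overview) and does not settle the matter.

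**The concern.** Three levels give three pairs, and the sequence holds only two of them. The missing pair is one message against none. A non-significant 2 vs 1 result does not show that one message works, so if the second message adds little, the sequence ends with two messages better than none and no protected decision on one. That is the situation in which a reader would most want to know whether a single message is enough.

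The adjusted pairwise tests in the Analysis section could fill the gap, but they are a second scheme for the same trial. Neither section says which one is confirmatory. The choice affects which claims can be made and how much power each contrast has.

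**Working it through.** **Inputs.** From the protocol's MyChart table: 2% with no message; 10% and 20% with one and two standard messages; 20% and 30% with one and two tailored messages. There are 293 per group in five groups. Sidedness is not stated; two-sided reproduces the table.

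**The plan's own sizes.** With p̄ the mean of the two rates, n per group = [1.960·√(2p̄(1−p̄)) + 0.842·√(p1(1−p1)+p2(1−p2))]² / (p1−p2)².
- 10% vs 20%: 199 (stated 199).
- 20% vs 30%: 293.2 (stated 293).
- 10% vs 30%: 62 (stated 62).
- 293 × 4 = 1172 and 293 × 5 = 1465, as stated.

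The stated sizes therefore match unadjusted two-sided 0.05 tests.

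**Power formula.** Power = Φ[(|p1−p2| − z·s0)/s1], where s0 is the standard error under the pooled rate, s1 the standard error under the separate rates, and z = 1.960 at 0.05 or 2.807 at 0.005.

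**1 vs 0 at the planned size.**
- Weakest cell, 10% vs 2%, 293 each: s0 = 0.01962, s1 = 0.01934; (0.08 − 0.03846)/0.01934 = 2.148; power 98.4%. Only 138 per group would be needed for 80%.
- Pooled over message type, (10%+20%)/2 = 15% with 586 vs 2% with 293: power above 99.9%.

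**2 vs 1 when the second message adds less than planned.** Pooled, 586 vs 586, starting from 15%. The gains of 0, 3 and 5 points are assumptions.

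| Two-message rate | (difference − 1.960·s0)/s1 | Significant in favor of two |
|---|---|---|
| 15% | −1.960 | 2.5% |
| 18% | (0.03 − 0.04250)/0.02167 = −0.577 | 28% |
| 20% | (0.05 − 0.04351)/0.02215 = 0.293 | 62% |
| 25% (planned) | (0.10 − 0.04580)/0.02318 = 2.338 | 99% |

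**The Analysis section's route.** The method is unnamed, so take Bonferroni over the 10 pairs of five groups as an illustration: 0.05/10 = 0.005.
- 10% vs 2%: (0.08 − 2.807 × 0.01962)/0.01934 = 1.289; power 90%.
- 30% vs 20%, 293 each: s0 = 0.03578, s1 = 0.03554; (0.10 − 2.807 × 0.03578)/0.03554 = −0.012; power about 50%. At 0.05 it is 80%.

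**Error rate if 1 vs 0 joins 2 vs 1 in the second step.**
- If 2 = 0 is true, any error must begin with a false rejection of 2 vs 0, which has probability at most 0.05.
- If 2 = 0 is false, 2 = 1 and 1 = 0 cannot both be true, since together they imply 2 = 0. At most one true null is then tested, at 0.05.

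The familywise error for this factor is therefore at most 0.05, provided each test holds its level. A simulation of 400,000 runs gave 0.050 when all three rates are equal and 0.049 when two equals one and both exceed none.

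**The case against.** The strongest reply is that the Analysis section already covers 1 vs 0. Its sentence also governs the Televox trials, which are sized for contrasts that include a no-message arm, so that arm most naturally belongs to the pairwise set. The MyChart no-message group has 293 subjects, and the protocol's Response variables give untreated groups their own completion rule. Under the Bonferroni illustration, power for one standard message vs none is still 90%, and for one tailored message vs none it exceeds 99.9%. This stands. A reader might infer from the sequence that the trial can never confirm that one message beats none, and the documents do not support that reading.

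The reply does not remove the problem. The sequence is the only scheme tied to a stated error rate. Using the pairwise tests as the route to 1 vs 0 may also weaken a contrast that the protocol says is fully powered.

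It is also fair to say that the plan expects a 10-point gain from the second message, where 2 vs 1 has 99% power. The gap matters only if that expectation is optimistic.

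Finally, a reader might call one message the cheapest strategy. The documents give no cost for MyChart messages; the cost remark in the sample-size section concerns personal contacts.

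**Conclusion.** The point holds as an omission in the fixed sequence together with two unreconciled multiplicity schemes. It does not hold as a claim that the trial is unable to test one message.

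The sequence yields no decision on 1 vs 0 under any result. This matters most when the second message adds little: at assumed gains of 0, 3 or 5 points, the sequence fails to favor two messages over one about 97.5%, 72% or 38% of the time (100% minus 2.5%, 28% and 62%), and it then says nothing protected about one.

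The figures rest on equal-weight pooling over message type, which the protocol does not specify for the sequence, and on the planned 293 per group. The fall from 80% to about 50% depends on Bonferroni over 10 pairs, which is an assumption. The 0.05 bound covers the number-of-messages factor for one outcome, not the whole trial.

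**What to change.** In Power/Sample Size, MyChart Trial, replace the sequence with: test 2 vs 0 at two-sided 0.05; if significant, test both 1 vs 0 and 2 vs 1, each at two-sided 0.05. State whether these tests pool over message type. If they are run within each type instead, the 0.05 bound applies within each type only.

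In Analysis, state that this sequence is the confirmatory scheme for the number of MyChart messages and that the adjusted pairwise tests do not replace it. Name the adjustment method and say whether the no-message group is in the pairwise set.

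The cost is a few sentences. No subjects are added, and 2 vs 1 keeps its present level and power. Two other placements cost more:
- 1 vs 0 last, after 2 vs 1: it is reached and passed only about 5% of the time when the second message adds nothing.
- 1 vs 0 between the two present steps: 2 vs 1 goes untested about 8% of the time if one message gives 7% vs 2% (an assumed case, 586 vs 293, power 91.7%). This waiting buys no error control.
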